7. APPENDICES

Appendix 1: IQPP Standard for Recording Donor Adverse Events

IQPP Standard for Recording Donor Adverse Events	لیہ Por IQPP_DAERS_V2.pdf
--	---------------------------------

Statistical Analysis Plan Version: 1.0 Date: 26-Apr-2020

Appendix 2: Assumptions for Sample Size estimation

PATIENT ID

100,000 Pat_ID are generated starting from 1 to 100,000 (size of population).

GENDER

The variable *Gender* is generated using *Female ratio* = 0.357 as mean. *Gender* follows Binomial distribution:

Gender ~ B(0.357)

Where Gender = 1 for females, Gender = 0 for males.

WEIGHT

The variable Weight follows Truncated Normal distribution with the following parameters:

Maximum weight: $W_{max} = 400$ lbs

Minimum weight: $W_{min} = 110$ lbs

Average weight: $\mu_{Weight} = 211.2$ lbs

Standard deviation of weight $\sigma_{Weight} = 50.85$

The assumptions were used based on the clinical site historic information provided

byHaemonetics.

HEIGHT

Similar, the variable *Height* follows Truncated Normal distribution with the following parameters:

Maximum height: $H_{max} = 84$ inches

Minimum height: $H_{min} = 56$ inches

Average height: $\mu_{Height} = 68.76$ inches

Statistical Analysis Plan Version: 1.0 Date: 26-Apr-2020

Standard deviation of height $\sigma_{Height} = 3.86$

The assumptions were used based on the clinical site historic information provided by

Haemonetics.

BODY MASS INDEX (BMI)

BMI is calculated for each patient using the following formula:

$$BMI = \frac{Weight(lbs)}{Height^2 (in)} \times 703$$

AGE

The following proportions of donors are included in the age categories described in Table 1.

Table 1: Age distribution of patients.

Age	18-20	21-24	25-44	45-64	65+
Proportions	0.0669	0.1512	0.5235	0.2530	0.0054

When generating ages for the patients we assume that the ages of patients are distributed uniformly within the categories.

ARM

The variable *Method* is generated using *Experimental method ratio* = 0.5 as mean. *Method* follows Binomial distribution:

Method ~ B(0.5)

Where Method = 1 for experimental arm, Method = 0 for standard arm.

NUMBER OF DONATIONS PER PATIENT

Average number of donations per patient is assumed to be 4. Thus, the expected number of occurrences $\lambda = 4$. Number of donations follows Truncated Poisson distribution with the Protocol No: TP-CLN-100467(AB)

ClinStatDevice

Statistical Analysis Plan Version: 1.0 Date: 26-Apr-2020

following parameters: $\lambda = 4$, minimum number of donations equals 1, maximum equals 24, since FDA recommends that donors must not undergo plasmapheresis more frequently than once in a 2day (48 hours) period or twice in a 7-day period.

FIRST COMERS

The variable *First comer* is generated from Binomial distribution with the mean parameter μ_{first} *comer* = 0.146:

First comer ~ $B(\mu first comer)$

Where *First comer* = 1 for first comers, *First comer* = 0 for repeat donors.

GENERATION OF ADVERSE EVENTS

AEs for the patients are generated using the method of Emrich and Piedmonte for correlated binary data.

The corresponding function for generating AEs uses the mean vector *Mean AE*, and the correlation matrix *Corr AE* to generate AEs for the patients. Correlation between first donation and other donations within a patient is assumed to be 0.1, while the correlation between repeat donations is assumed to be 0.5.

For example, correlation matrix Corr AE for a patient with 4 donations is:

$$Corr \ AE = \begin{bmatrix} 1 \ 0.1 \ 0.1 \ 0.1 \ 0.1 \\ 0.1 \ 1 \ 0.5 \ 0.5 \\ 0.1 \ 0.5 \ 1 \ 0.5 \\ 0.1 \ 0.5 \ 0.5 \ 1 \end{bmatrix}$$

Average rates of AEs for the age groups are presented in the Table 3.

Table 3: Adverse event distributions by age groups of patients.

Age	18-20	21-24	25-44	45-64	65+
AE rates	0.004579	0.002165	0.0011	0.000827	0.000951

Statistical Analysis Plan Version: 1.0 Date: 26-Apr-2020

The mean vector *Mean AE* for a patient with 4 donations includes 4 values, which can be found using the following equation:

 $Mean AE = \beta_{Age} * Age + \beta_{Gender} * Gender + \beta_{Method} * Method + \beta_{First Comer,Female} *$ $(First Comer, Female) + \beta_{First Comer,Male} * (First Comer, Male)$

Where coefficient β_{Age} takes the five values of AE rates described in Table 2. Average AE rate is 0.003831 for females, and 0.001145 for males, so $\beta_{Gender} = 0.003831 - 0.001145 = 0.002686$. The study also demonstrates that average AE rate is 0.01302 for female first comers, compared to 0.002098 for female repeat donors, thus $\beta_{First \ comer,Female} = 0.01302 - 0.002098 = 0.010922$. Average AE rate is 0.003061 for male first comers, compared to 0.002581.

Additionally, we assume that donors stop the plasmapheresis after having an AE.

Table 4: *Comparison of variable values in the population data and theoretical targets/historical estimates.*

Variable name	Population data 0 difference of AEs between arms	Population data 0.0015 difference of AEs between arms	Target / historical estimate
Difference of AEs between arms	0.000001228461	0.001518541	0/0.0015

Statistical Analysis Plan Version: 1.0 Date: 26-Apr-2020

Proportion of females	0.3570712	0.3578287	0.357
Average weight in lbs	213.7896	214.1136	211.2
Average height in inches	68.76917	68.75169	68.76
Proportion of people with age 18-20	0.06798374	0.06786572	0.0669
Proportion of people with age 21-24	0.1494797	0.1505201	0.1512
Proportion of people with age 25-44	0.5237046	0.5253826	0.5235
Proportion of people with age 45-64	0.2533512	0.2502998	0.2530
Proportion of people with age 65 and above	0.00548081	0.005931791	0.0054
Proportion of donors in experimental arm	0.4989608	0.4954739	0.5
Number of donations per patient	4.055597	4.04431	4
Proportion of first comers	0.14677	0.14501	0.146
AE rates for age group 18-20	0.003010082	0.003825555	0.004579
AE rates for age group 21-24	0.001789587	0.002595483	0.002165
AE rates for age group 25-44	0.00134408	0.002127249	0.0011
AE rates for age group 45-64	0.001201847	0.001669482	0.000827
AE rates for age group 65 and above	0.0002249213	0.002084202	0.000951
β_{Gender}	0.001733372	0.001720488	0.002686
$eta_{First\ comer,Female}$	0.01431423	0.01592894	0.010922
$eta_{First\ comer,Male}$	0.003890562	0.003096266	0.002581

Protocol No: TP-CLN-100467(AB)

Page 34 of 34

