## 6.1.3 Subject Withdrawal

Subjects will not be considered for further donations if any of the following occurs:

- Subject not able or willing to give consent to participate in the clinical trial.
- Subject donated plasma outside of the present clinical trial after enrolling in this clinical trial.
- Subjects are withdrawn from the clinical trial due to safety concerns by the qualified healthcare providers.
- In addition, all donors for whom a BMI for use in the PPN feature cannot be reliably calculated will be excluded.

Subject withdrawal for any reason will be documented on the Subject Withdrawal Log.

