#### 7.1 Clinical Trial Duration

Enrollment will be approximately 4 to 6 months. Prior to enrollment, all subjects will be required to provide written consent. Once enrolled, all subjects will remain in the clinical trial for their first and any subsequent donations per institutional guidelines until enrollment is completed or until they withdraw consent. For each subsequent donation, subjects will be required to meet all eligibility criteria (see eligibility criteria below). Subjects will be followed up according to established site procedures. The plasmapheresis procedure will follow standard of care practices at the centers, with the exception that the target plasma collection volume is determined per the PPN feature in the experimental group.

Monitoring of adverse events (AEs) will be conducted throughout the clinical trial. All AEs will be captured and reported per established site procedures in compliance with IQPP standards and with CFR. Reporting of AEs in study subjects will occur after the subject's donation has ended per established site procedures. The safety of the clinical trial will be monitored by a Data Monitoring Committee (DMC) which will meet regularly and will be operating according to the DMC charter.

The original assignment of the subject to the experimental group or to the control group, respectively, will be carried over. There will be no re-randomization for repeat donors.

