#### 7.2.1 Inclusion Criteria

Donors must be qualified to donate plasma per individual site's screening procedures which are in compliance with IQPP standards (see Appendix 16.2 IQPP Qualified Donor Standard). If donors do not meet inclusion criteria at subsequent donations but have already been enrolled in the clinical trial, they are eligible to remain in the clinical trial and to donate plasma within the clinical trial once they meet eligibility criteria again, except if they fulfill any of the exclusion criteria listed below.

Other site-specific regulations and procedures may apply.

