4. INTERIM ANALYSIS

One interim analyses may be conducted, when data from 16,000 apheresis procedures will be available. The interim analysis may result in sample size re-estimation of the sample size in accordance with the promising zone approach. It can be increased to include up to approximately 30,000 donations. Maximum 7,500 donors might be included.

Early termination of the trial due to safety concerns may be possible, when collected data at the interim analysis will provide strong evidence against establishment of non-inferiority at the end of the trial.

Statistical Analysis Plan Version: 1.0 Date: 26-Apr-2020

Should the formal interim analysis be conducted, the exact boundaries and decision rules will be finalized at least one week prior to interim analysis unblinding. The SAP will be amended to accommodate these additions.

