5. SAMPLE SIZE CONSIDERATIONS

In order to evaluate the operating characteristics of the study design and the analysis methodology, extensive Monte-Carlo simulation study was conducted. The experiment was designed with an objective to mimic the real study as closely as possible (with assumptions presented in Appendix 3). The historic data on significant hypotensive AE rates, study population demographics, first-time donor status etc. was analyzed to inform the simulation study.

This experiment evaluated the relationship between number of subjects, number of donations and the probability of rejecting the null hypothesis for the various assumptions of the true AE rates. Type I error was evaluated for multiple scenarios when the true AE rate of the experimental arm was unacceptably large: $P_{Exper} - P_{Ctrl} > \delta$

NI margin δ is set at level of 0.0015 (0.15%). For the power analysis, 5,000 simulations were conducted and power was calculated as follows:

$$Power = \frac{N(reject H_0)}{N_{sim}} * 100\%$$

Power is calculated for rejecting H_0 at significance level of 2.5% (using 97.5% one-sided CI for the AE rate difference).

Statistical Analysis Plan Version: 1.0 Date: 26-Apr-2020

Incidence rate of AE in the experimental group is assumed to be 0.0015 (0.15%). The total sample size of 6,000 subjects (3,000 per group) with an expectation of 24,000 total donations yields acceptable profile of power and type I error.

In the scenario when the experimental procedure is at least as safe as the standard one there is greater than 85% power to establish the NI.

Type I error is below 2% for the scenario when $P_{Exper} - P_{Ctrl} = 0.00175$ and is as low as ~ 1% for

 $P_{Exper} - P_{Ctrl} = 0.0020.$

Performance of the estimation method during the simulations in terms of statistical power for detecting difference in levels of significant AE incidence rate in experimental versus control groups, given the δ =0.0015, in various scenarios is presented below in Table 1.

Table 1: Performance of estimation method using 24,000 plasmapheresis procedures.

PExper – PCtrl	≤0	0.0005	0.00075	0.0010	0.0015	0.00175	0.0020
Power	>85%	68.4%	49.4%	28.5%	5.7%	1.9%	1.1%

Statistical Analysis Plan Version: 1.0 Date: 26-Apr-2020

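### The SAP's >85% power holds only if donors stop after an event, given its own within-donor correlations of 0.1/0.5; section 5 does not say so and the visible protocol text does not secure it

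*SAP*

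**What the plan says.** SAP section 5 reports a Monte Carlo study with 6,000 donors and an expected 24,000 donations. If the experimental procedure is at least as safe as control, "there is greater than 85% power to establish the NI". For its inputs it refers the reader elsewhere: "with assumptions presented in Appendix 3". The inputs are in fact in Appendix 2. That appendix sets a correlation of 0.1 between a donor's first donation and later ones, and 0.5 among later ones. It then adds: "Additionally, we assume that donors stop the plasmapheresis after having an AE". Table 1 varies only the true difference.

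The visible text on whether a donor comes back reads as follows.

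- Protocol 7.1: "all subjects will remain in the clinical trial for their first and any subsequent donations per institutional guidelines until enrollment is completed".
- Protocol 7.2.1, on donors who fail inclusion at a later visit: "they are eligible to remain in the clinical trial and to donate plasma within the clinical trial once they meet eligibility criteria again".
- Protocol 6.1.3 lists, among the grounds for no further donation: "Subjects are withdrawn from the clinical trial due to safety concerns by the qualified healthcare providers".
- SAP 2.2.2 puts every started study donation in the ITT set, so later donations and repeat events would count.

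On the event rate, SAP section 5 attaches 0.0015 to the experimental group.

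**The concern.** A correlation of 0.5 between a donor's repeat donations should cost a lot of power, yet the stated power is what independent donations would give. The stopping sentence explains this: with at most one event per donor, no donor can show clustered events. The second assumption therefore cancels the cost of the first.

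No visible passage requires a donor to leave after an adverse event. If donors return and events cluster within donors, the chance of missing non-inferiority with equally safe arms is larger than the simulation shows, and a reader of section 5 cannot see that its figure is conditional. The arm label is a separate difficulty: it decides which event rate the simulation held fixed.

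**Working it through.** **Inputs.** One-sided 2.5%, margin 0.0015, 3,000 donors and about 12,000 donations per arm, rate 0.0015 in both arms at zero difference (SAP 5). Wald upper limit (SAP 3.1.1). Donations per donor truncated Poisson, λ = 4, range 1–24; correlations 0.1/0.5 (Appendix 2).

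**1. The plan's own figure.** For independent donations:

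- SE = √(2 × 0.0015 × 0.9985 / 12,000) = 0.000500
- Power = Φ(0.0015/0.000500 − 1.96) = Φ(1.04) = 85.1%

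A simplified simulation (latent-normal correlated binary events, donor-clustered Wald limit, correlations 0.1/0.5, stopping after the first event, observed rate about 0.0015) gives about 86%, with an estimated within-donor correlation near zero. The stated figure reproduces.

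**2. Every donor returns, correlations 0.1/0.5.** For m donations the variance of a donor's event count is p(1−p)[m + 0.2(m−1) + 0.5(m−1)(m−2)].

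- E[m] = 4/(1 − e⁻⁴) = 4.0746; E[m²] = 20/(1 − e⁻⁴) = 20.373
- E[(m−1)(m−2)] = 20.373 − 12.224 + 2 = 10.149
- Design effect = (4.0746 + 0.2 × 3.0746 + 0.5 × 10.149)/4.0746 = 2.396
- SE = 0.0004996 × √2.396 = 0.000773
- Power = Φ(1.94 − 1.96) = 49%

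Simulations at the same observed rate give 53–60%, with about 7 donors per trial having two or more events. If the generating rate that yields 0.0015 under stopping is held fixed instead, the observed rate rises to about 0.0023 and power is 38–42%. A re-run must therefore say which rate it fixes.

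**3. Every donor returns, lower correlations.** For exchangeable correlation r the design effect is 1 + r·E[m(m−1)]/E[m] = 1 + 4r.

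| r | Design effect | Formula power | Simulated power |
|---|---|---|---|
| 0 | 1.00 | 85% | 85% |
| 0.05 | 1.20 | 78% | about 79–81% |
| 0.1 | 1.40 | 72% | about 73–75% |

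With no correlation nothing is lost, so the loss needs both return and clustering.

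**4. How firm the 85% baseline is.** Inverting Table 1 with SE = (0.0015 − d)/(1.96 + z), where z is the normal quantile of the stated power:

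- d = 0.0005, 68.4%: 0.0010/(1.96 + 0.48) = 0.00041
- d = 0.00075, 49.4%: 0.00075/(1.96 − 0.015) = 0.00039
- d = 0.0010, 28.5%: 0.0005/(1.96 − 0.57) = 0.00036

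These imply zero-difference power from Φ(0.0015/0.00041 − 1.96) = 96% to Φ(0.0015/0.00036 − 1.96) = 99%, which is also above 85%. The step 1 formula (0.0015 as control rate) gives 46%, 27% and 14% in those columns, so it matches Table 1 only at zero difference. Multiplying the implied SEs by the square roots of the design effects gives, roughly, 92–97% (r = 0.05), 87–94% (r = 0.1) and 66–77% (0.1/0.5).

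**5. What stopping means here.** The sentence could mean only that the procedure is ended. Table 4's second column shows 4.04431 donations per donor. The mean without stopping is 4.0746, with SE 1.942/√100,000 = 0.0061, so the printed value is 4.9 SE lower. That fits stopping of further donations. The first column (4.055597) is not used: times 100,000 it is not a whole number, so its denominator is unclear.

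**6. Which arm has 0.0015.** If it is the experimental arm, Table 1's last two columns need control rates of 0.0015 − 0.00175 = −0.00025 and 0.0015 − 0.0020 = −0.0005. In Table 4 at difference 0.0015, age shares times age-specific rates sum to 0.00026 + 0.00039 + 0.00112 + 0.00042 + 0.00001 = 0.00220. With 0.4955 of donors in the experimental arm, the control rate is about 0.00220 − 0.4955 × 0.00152 = 0.00145. Table 4 thus suggests that 0.0015 is the control rate.

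**The case against.** The assumption is disclosed: an appendix devoted to sample-size assumptions states it, and section 5 points to an appendix, though by the wrong number. That stands; what is missing is the condition beside the power figure and any variation of it.

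Centers may also enforce stopping. Continuation is subject to institutional guidelines, Protocol 7.2.1 allows for site-specific rules, and Protocol Appendix 16.2 is not visible. Protocol 7.2.2 makes exclusion after a safety withdrawal permanent, and Protocol 9.9 and SAP 3.5 plan to report events that trigger withdrawal. Some event-driven stopping is therefore expected, and full return is a bound. The protocol does not contradict the assumption; its visible text simply does not guarantee it.

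A correlation of 0.5 is strong: one event at a repeat donation implies roughly an even chance at each other repeat donation. But it is the SAP's own input, and SAP 3.1.1 says the correlation model is still being derived.

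A reader might infer that any return with any clustering pushes the chance of a miss above 15%. The documents do not support that. The SAP states a lower bound, and step 4 shows that power could stay above 85% at correlations of 0.05–0.1. A reader might also want a figure for half of donors returning. None is given here, because half can mean half of events or half of donors and the answers differ.

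Finally, the interim analysis may raise the sample size: "It can be increased to include up to approximately 30,000 donations". That step is optional. With 15,000 donations per arm, full return and 0.1/0.5, SE = √(2.396 × 2 × 0.0015 × 0.9985/15,000) = 0.000692 and power is Φ(2.17 − 1.96) = 58%.

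**Conclusion.** The point holds in a limited form. The stated power is conditional on donors stopping after an event, given the SAP's own 0.1/0.5 correlations. Section 5 does not say so, and nothing visible secures it. At an observed rate of 0.0015 and about 24,000 donations, power is about 86% with stopping and about 49–60% with full return. Even on the more favourable baseline implied by other Table 1 columns, full return under 0.1/0.5 gives roughly 66–77%. At exchangeable 0.05–0.1 the simplified model gives about 72–81% from an 85% baseline, but the sponsor's baseline is not pinned down, so a fall below 85% is not established there.

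It would be wrong to conclude that the trial's actual power is about one half: the documents give no return rate, and full return is the extreme case. The validity of the donor-clustered analysis is not in question. The conflict over which arm carries 0.0015 stands on its own.

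**What to change.** - Reconcile the stopping assumption in SAP Appendix 2 with the protocol's continuation and withdrawal text. Whether donors return is a clinical and site matter on which this point takes no position.
- Re-run the sponsor's own simulation with no return, with full return, and at a historical or explicitly defined partial return rate (per event or per donor). Use 0.1/0.5 and lower correlations such as exchangeable 0.05 and 0.1, and state whether the pre-stopping or the observed event rate is held fixed.
- Restate the power in SAP section 5 as conditional on return after an event and on within-donor correlation, with the figure for each case.
- Correct the appendix reference, and reconcile which arm the 0.0015 rate belongs to across section 5, Table 1 and Table 4.

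The cost is a simulation re-run, some SAP wording, and a power figure that is conditional and possibly lower. Correcting the statement needs no change to enrolment.
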